### 7.2.4.1. Visit 3 (Day 22 ±3 Days)

To accommodate PK sample collection at Visit 3, patients will be instructed to not take their daily dose of study drug before arriving at the study site; patients will bring their study drug and study diary with them to the study visit (time of study drug administration on the day before Visit 3 should be recorded in the study diary).

Study drug administration will be at the study site and timing will be based on timing of the PK sampling and 12-lead ECGs.

12-lead ECGs and blood sample collection for PK analyses:

- Holter monitor should be placed on the patient and continuous recording started as ECG data are taken from the Holter recording.
- 12-lead ECGs (in triplicate) and a blood sample collection for PK analyses will be performed before study drug is administered (the time of the ECG and blood sample collection for PK must be recorded). The ECGs should be done prior to and within 15 minutes of the pre-dose blood sample collection for PK analyses.
- After the 12-lead ECGs and PK sample collection are completed, patients will be administered study drug (the time of study drug administration must be recorded).
- Additional 12-lead ECGs and blood sample collection for PK analyses will be performed at 3 hours (±30 minutes) after dosing (the time of each ECG and blood sample collection for PK must be recorded). The ECGs should be done prior to and within 15 minutes of the post-dose blood sample collection for PK analyses.

The following assessments will also be performed at Visit 3:

- Urine pregnancy test (FCBP only)
- Abbreviated physical examination (Section 6.3.2)
- Vital signs (Section 6.3.3)
- Clinical laboratory tests (serum chemistry, hematology, urinalysis) (Table 8)
- Review of AEs
- Review of concomitant medications
- C-SSRS (Since Last Update; Appendix D)
- Review study drug compliance/accountability (Section 5.5 and Section 5.6)
- 24-hour Holter monitoring

Patients will be dispensed study drug in a sub-kit for Week 4 through Week 7.

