### 9.2.2 Data Selection for Multiple Results

**Double-Blind Treatment Phase:** For post-baseline assessments, if there are multiple non-missing results within the same analysis window (including scheduled and unscheduled results), then the non-missing result that is closest to the target date will be used in the analyses; if more than one result is equally close, the result that is after the target date of the assessment will be used. If necessary, time of the assessment (if collected) will be used to determine the record to be selected.

**OLE Phase:** Assessments performed at nominal visits will be used in the analyses/summaries. Unscheduled assessments will only be used to determine worst, lowest and/or highest results post-baseline where applicable.

Twelve-lead ECGs will be collected in triplicate at each nominal visit as prespecified in the protocol. The mean value of the triplicate (or duplicate) at each nominal visit will be derived. The rules defined above for the post-baseline assessments and for the baseline (section 9.3) will be applied to determine which mean values will be summarized. For the overall interpretation, the worst interpretation across the triplicate (or duplicate) for each given nominal visit will be selected first, and then the rules defined above for the post-baseline assessments and for the baseline (section 9.3) will be applied to determine the results to be summarized.

---

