### 11.6.6 12-Lead Electrocardiograms

Triplicate 12-lead ECGs will be obtained after the patient has been resting for at least 5 minutes. For clinically significant ECG findings, a follow-up ECG should be performed within 24 hours and again 7 days later to ensure that the abnormality is not worsening. Follow-up 12-lead ECGs may be performed locally and sent to the Investigator for assessment; the Investigator will submit all ECGs done locally to the central ECG vendor.

A core ECG laboratory will manage all ECG monitoring activities. All ECG results along with the investigator's interpretation, including the average of triplicate measurements at each timepoint, will be presented in data listings.

QT values will be presented with the implementation of corrections (i.e., Fridericia's) as defined in International Council for Harmonisation (ICH) Guidelines E14 by the following categories:

Absolute QT interval corrected for heart rate based on Fridericia's formula (QTcF) interval prolongation:

- QTcF interval <450 ms
- QTcF interval 450-480 ms
- QTcF interval 480-500 ms
- QTcF interval >500 ms

Change from baseline in QTcF interval:

- QTcF interval increases from baseline 30-60 ms
- QTcF interval increases from baseline >60 ms

In addition, potential QT prolongations will be categorized as:

- PR interval >300 msec
- QRS duration >140 msec
- PR interval increase from baseline >50%
- QRS duration increase from baseline >40%

- HR increase >65% from baseline
- HR decrease >40% from baseline

The actual values and change from baseline values at each time point will be summarized for the safety populations. The overall interpretation will also be summarized by timepoint as well as the worst post-baseline.

The average of the triplicates at each timepoint will be used in the summaries as defined in [Section 9.2](#).

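### SAP 9.2.2 keeps one ECG mean per visit window, so either the pre-dose or the 3-hour set at Visits 3 and 5 can drop out of the ECG summaries

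*SAP*

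**What the plan says.** **Protocol.** Section 6.3.4.2 pairs a triplicate ECG with every PK blood sample at Visits 3 and 5. Sections 7.2.4.1 and 7.2.4.4 place the first set before dosing. For the second they say "Additional 12-lead ECGs and blood sample collection for PK analyses will be performed at 3 hours" after dosing, give or take 30 minutes, which Section 6.4 takes as tmax. Visit 4 has a single set.

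**SAP 9.2.2.** In the Double-Blind Treatment Phase, scheduled and unscheduled results in a window compete, and "then the non-missing result that is closest to the target date will be used in the analyses". A tie goes to the result after the target date. The last resort is: "If necessary, time of the assessment (if collected) will be used to determine the record to be selected". For ECGs, "The mean value of the triplicate (or duplicate) at each nominal visit will be derived", and the same rules "will be applied to determine which mean values will be summarized".

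**SAP 11.6.6.** On the measured intervals and heart rate, the section promises summaries by time point: "The actual values and change from baseline values at each time point will be summarized for the safety populations". A worst-case summary appears only for the reading of the tracing, where the SAP says: "The overall interpretation will also be summarized by timepoint as well as the worst post-baseline". On the unit of analysis it points back to Section 9.2: "The average of the triplicates at each timepoint will be used in the summaries as defined in". All ECG results and the triplicate averages per timepoint go into listings. The section sets QTcF categories (up to >500 ms absolute; increases of 30-60 and >60 ms) and thresholds for PR, QRS and heart rate, but does not name the record that feeds them.

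**SAP Tables 5 and 6.** Table 5 has one row per visit and no dose-relative level. Table 6 does list pre-dose and 3 hours post-dose, but as PK draw times.

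**The concern.** Two sections of the SAP use different units for the same data. Section 9.2.2 works by nominal visit and keeps one record per window. Section 11.6.6 works by timepoint and then hands the definition back to 9.2. A programmer who follows 9.2.2 to the letter summarizes one ECG mean at Visits 3 and 5, where the protocol collected two.

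Safety is part of the primary objective, Protocol 1.4 states that pitolisant prolongs the QT interval, and triplicate ECGs are among the mitigations named there. Visits 3 and 5 are the only scheduled visits with an ECG timed to peak concentration. The 3-hour values should therefore not depend on how a programmer settles a tie.

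**Working it through.** The plan states no figure on this point, so there is none to reproduce. The check is a comparison of rules plus simple arithmetic.

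**1. Sets against windows** (double-blind, post-baseline, scheduled)

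| Visit | Triplicate sets (protocol) | Records kept by SAP 9.2.2 and Table 5 |
|---|---|---|
| 3 (Day 22) | 2: pre-dose, 3 h | 1 |
| 4 (Day 49) | 1 | 1 |
| 5 (Day 77) | 2: pre-dose, 3 h | 1 |
| Total | 5 | 3 |

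Read literally, 5 − 3 = 2 sets are not summarized, one at each dose-timed visit. Read by timepoint, as 11.6.6 suggests, all 5 are kept.

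**2. Which set is lost.** Both sets carry the same date, so distance to target cannot separate them. The preference for a result after the target date cannot either. That leaves clock time, and the SAP does not say whether the earlier or the later record wins.

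**3. Does 11.6.6 settle it?** Not by itself. It defines no ECG timepoint and points to Section 9.2, where the ECG paragraph works by nominal visit. SAP 11.6.7 uses the same time-point sentence for Holter data, where there is one recording per visit, so the term does not by itself mean pre-dose and post-dose. A worst post-baseline summary is promised only for the overall interpretation, not for QTcF, PR, QRS or heart rate.

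**4. Unscheduled ECGs.** Protocol 6.3.4.2 calls for a repeat within 24 hours of a clinically significant finding and again 7 days later. The Visit 3 window is Days 2 to 35.

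- Visit on Day 21, repeat on Day 22: distances |21 − 22| = 1 and |22 − 22| = 0. The repeat is kept and both scheduled sets are dropped.
- Visit on Day 22, repeats on Days 23 and 29: distances 0, 1 and 7. Both repeats are dropped.

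SAP 9.2.2 uses unscheduled results for worst, lowest or highest values, but says so only for the OLE Phase.

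**5. Size.** The documents give no QTcF effect. Let g be the 3-hour minus pre-dose difference, assumed to lie between 5 and 30 ms.

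- 3-hour set kept: the 3-hour value is understated by 0.
- Pre-dose set kept: it is understated by g, that is 5 to 30 ms. A 3-hour increase above 60 ms and up to 60 + g misses the >60 ms category, so the upper end of that gap is 65 ms (g = 5) to 90 ms (g = 30).
- Effect on a rate: about 30 patients at 1:1:1 is about 10 per arm, so one uncounted patient is 1/10 = 10 percentage points in that arm, or 1/20 = 5 points in the pooled active group.

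**The case against.** The strongest reply is that 11.6.6 is the ECG analysis section and speaks of timepoints for values, changes, interpretation and listings. Its cross-reference is to Section 9.2 as a whole, which includes Table 6, and Protocol 6.3.4.2 ties the ECGs to those same PK draws. On that view the intent is plain and only the wording is loose. This is a fair account of the likely intent. It does not remove the conflict: Table 6 is confined to PK draws, and the one paragraph in 9.2 written for ECGs says nominal visit and sends the means through the one-record rule.

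A reader might infer that the pre-dose and 3-hour sets are averaged together. The documents do not support that. Section 9.2.2 speaks of a triplicate or duplicate, meaning three or two tracings rather than six, and of choosing among mean values in the plural, so separate means exist before selection.

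A reader might also infer that QT effects are certain to be understated. That does not follow: if the later record wins the tie, the 3-hour value survives and the pre-dose value is the one lost.

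It is also fair to say that safety reporting is descriptive, and that using the worst value for every category goes beyond reconciling two sections. The second remark holds, and the fix below presents that part as a rule to be chosen.

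**Conclusion.** SAP 9.2.2 and 11.6.6 are in conflict and should be reconciled. Taken literally, 9.2.2 drops one of two ECG sets from the summaries at each of Visits 3 and 5, so 2 of the 5 scheduled post-baseline double-blind sets, with no stated rule for which. The 3-hour values, and unscheduled ECGs further from the target day, may therefore be missing from the QTcF, PR, QRS and heart-rate summaries and outlier counts. The loss in QTcF runs from nothing to the full difference between the two sets (0 to 30 ms, taking an assumed difference of up to 30 ms).

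It would go too far to say that the plan conceals QT prolongation. Every ECG result and per-timepoint average is listed, the overall interpretation has a worst post-baseline summary, and the discontinuation rule in Protocol 4.4.1 acts on any qualifying ECG finding, whatever the SAP tabulates. The weakness lies in the prespecified summary tables, not in the monitoring of individual patients.

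**What to change.** - **SAP 9.2.2:** state that at Visits 3 and 5 the triplicate mean is derived and selected separately for pre-dose and 3 hours post-dose, and that both are summarized.
- **SAP 11.6.6:** define ECG timepoint in the same terms, and state that the QTcF, PR, QRS and heart-rate categories use the worst post-baseline value across all timepoints, including post-dose and unscheduled ECGs. This extends to the Double-Blind Treatment Phase the use of unscheduled results that 9.2.2 already allows in the OLE Phase.

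The cost is SAP wording and a few extra table rows, with no new data and no change in conduct. Outlier counts may come out slightly higher, since a worst-value rule can only add cases. The rule should be fixed before the double-blind data are unblinded.

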## 9.3 Baseline

For the Double-Blind Treatment Phase, Baseline is defined as the last non-missing record or measure collected prior to the study drug administration. For the OLE phase, Baseline will be identical to the Double-Blind Treatment Phase (i.e., the last non-missing record or measure collected prior to study drug administration).

## 9.4 Double-Blind and OLE Analyses Reporting

The data collected for the Double-Blind Treatment Phase and the OLE Phase are included in the same database.

A data cut will be performed at the end of the Double-Blind Treatment Phase and another one will be performed at the end of the OLE Phase. The date of first dose in the OLE Phase will be used to determine if a patient entered the OLE Phase. A data cut-off will be applied to the datasets and only data related to the Double-Blind Treatment Phase will be reported:

- Baseline and baseline characteristics.
- Visits performed in the Double-Blind Treatment Phase, up to and including Visit 5 (Week 11) for patients who entered the OLE Phase, and up to the safety follow-up visits for patients who opt out of the OLE Phase.
- For patients who entered the OLE Phase, any adverse event (AE) or medication that started up to and including the last dose of study drug in the Double-Blind Treatment Phase. For this patient group a (any AE or medication that started after and up to 30 days after the last dose of study drug in the Double-Blind Treatment Phase will be reported in separate listings, i.e., they will be excluded from the Double-Blind Treatment Phase summary tables).
- For patients who opt out of the OLE Phase, all AEs and medications reported through the final 30-day safety follow-up telephone contact will be reported as part of the Double-Blind Treatment Phase.

The date of first dose in the OLE Phase will be kept in the datasets to determine if the patient has entered the OLE Phase.

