### 11.6 Safety Analyses

Safety analyses will be provided for the Double-Blind safety and open-label safety populations. All safety data will be listed and summarized. No formal statistics will be performed for the safety analyses.

For the Double-Blind Treatment Phase, summaries will be presented by treatment arms. For the OLE Phase, results will be tabulated by treatment received during the Double-Blind Treatment Phase (including active arms pooled) and overall.

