#### 11.6.1 Adverse Events

An AE is defined as any untoward medical occurrence associated with the use of a drug in humans, whether or not considered drug related.

A treatment-emergent AE (TEAE) is

- any AE reported after the first dose of study drug and up to 30 days after last dose of study drug, or
- any worsening of a pre-existing condition reported after first dose of study drug and up to 30 days after last dose of study drug.

For the OLE Phase, any AE starting on or after the first dose of OLE treatment will be considered treatment emergent.

A serious AE (SAE) is defined as any AE that results in any of the following outcomes: death, is life-threatening, results in inpatient hospitalization or prolongation of existing hospitalization, results in a persistent or significant incapacity or substantial disruption of the ability to conduct normal activities of daily living or is a congenital anomaly/birth defect. Important medical events that may not result in death, be life-threatening, or require hospitalization may be considered SAEs when, based upon appropriate medical judgment, they may jeopardize the patient and may require medical or surgical intervention to prevent one of the outcomes listed in this definition.

---

An AE's relationship to study treatment will be evaluated by the Investigator. The following relationships will be collected in eCRF: definitely related, probably related, possibly related, unlikely related, or not related. AEs that are evaluated as definitely, probably, or possibly related (or with missing relationship) will be considered treatment-related AEs for summary purposes.

The severity of AEs will be classified by the Investigator as mild, moderate, or severe. If the severity is missing, the AE will be assumed to be severe.

An overall TEAE summary will be generated presenting the frequency and percentage of patients and the number of AEs for the following:

- Any TEAE
- Any treatment-related TEAE
- Any severe TEAE
- Any treatment-related severe TEAE
- Any serious TEAE
- Any treatment-related serious TAE
- Any TEAE leading to study discontinuation
- Any TEAE leading to discontinuation of investigational product (IP)
- Any TEAE leading to interruption of IP
- Any TEAE leading to death

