All AEs will be coded using MedDRA; the version used will be included in the tables and listings footnotes. The TEAEs will also be summarized by system organ class (SOC) and preferred term (PT), by severity and relationship to study treatment.

The TEAE summary tables will be sorted by SOC and PT. SOC's will be displayed in descending order of overall frequency in the pooled pitolisant group and then alphabetically. PTs will be displayed in descending order of overall frequency and then alphabetically within SOC. A patient with 2 or more events within the same PT of summarization will be counted only once in that level using the most severe incident or most related incident. Percentages will be based on the number of patients in the safety population. The following summaries by SOC and PT will be provided:

- TEAE
- Treatment-related TEAE
- TEAE by maximum severity
- Serious TEAE
- Treatment-related serious TEAE
- TEAE leading to discontinuation of IP
- TEAE leading to interruption of IP
- TEAE leading to death

Finally, a summary of all AEs and all SAEs by SOC and PT will be provided.

All AEs will be presented in a data listing. Separate data listings will be generated for treatment related AEs, SAEs, and AEs leading to study discontinuation.

For patients who opt to continue in the OLE Phase of the study, only AEs started on or before the last dose of the Double-Blind Treatment Phase will be included in the summaries for the Double-Blind Treatment Phase. AEs started after the last dose of treatment and up to 30 days after the last dose of treatment in the Double-Blind Treatment Phase will be included in a separate listing and summarized in the OLE Phase reporting.

For clinicaltrials.gov and other registries, the following will be produced in XML format.

1. All-Cause Mortality: \*§ A table of *all* anticipated and unanticipated deaths due to any cause, with the number and frequency of such events by arm or comparison group of the clinical study.
2. Serious Treatment-Emergent Adverse Events: \* A table of *all* serious adverse events, grouped by System Organ Class, with the number and frequency of such events by arm or comparison group of the clinical study.

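### The double-blind TEAE tables pool two counting windows, set by OLE entry, so by-arm incidence can shift for reasons other than the drug

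*SAP*

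**What the plan says.** SAP 9.4 (Double-Blind and OLE Analyses Reporting) defines what enters the double-blind report.

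- **OLE entrants** contribute "any adverse event (AE) or medication that started up to and including the last dose of study drug in the Double-Blind Treatment Phase". Events that start later, up to 30 days after that dose, go to separate listings: "they will be excluded from the Double-Blind Treatment Phase summary tables".
- **Non-entrants** fall under a different rule: "For patients who opt out of the OLE Phase, all AEs and medications reported through the final 30-day safety follow-up telephone contact" belong to the double-blind report.

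SAP 11.6.1 repeats the cut for entrants ("only AEs started on or before the last dose of the Double-Blind Treatment Phase will be included in the summaries"). It adds that their later events are listed and also summarized with the OLE.

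The TEAE definition in 11.6.1 covers "any AE reported after the first dose of study drug and up to 30 days after last dose of study drug", so a non-entrant's off-drug events qualify as TEAEs.

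The denominator is a patient count: "Percentages will be based on the number of patients in the safety population". The overall TEAE summary also gives the number of events. SAP 11.6 states: "For the Double-Blind Treatment Phase, summaries will be presented by treatment arms". It also states: "No formal statistics will be performed for the safety analyses". Neither 9.4 nor 11.6.1 provides a common window, an exposure-adjusted rate or a supportive table. SAP 9.4 and 11.3.2 treat concomitant medications in the same two ways.

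**The concern.** Safety against placebo is part of the primary objective (Protocol 2.1; SAP 7.1), and the by-arm TEAE tables are where a reader will look for it. Which window a patient gets is settled after randomization. OLE entry is optional and requires eligibility to be confirmed at Visit 5. Tolerability or perceived benefit could plausibly influence it, although the documents do not say so. If the arms differ in how many patients enter, or in how many stop early, the arms are compared over different amounts of counted time. Off-drug events are also counted only for non-entrants. A descriptive table gets no later model adjustment, so the reader cannot separate this from a drug effect.

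The documents also leave open who is a non-entrant. Protocol 7.2.5 bars patients who stop before Day 77 from the OLE, whereas Protocol 3.1.1.3 lets them in with Medical Monitor approval. SAP 9.4 speaks of patients who opt out and does not expressly name early discontinuers.

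**Working it through.** The plan states no figure on this point, so there is nothing to reproduce. The check asks what the rule does when the true event hazard is the same in every arm.

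**Inputs from the documents.** Double-blind treatment lasts 11 weeks, or 77 days. Post-dose counting for non-entrants is 30 days. About 30 patients are randomized 1:1:1, so about 10 per arm.

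**Assumptions (not in the documents).** The 77-day TEAE risk p, the share e of an arm that enters the OLE, and a constant hazard. The off-drug hazard is either unchanged (upper case) or halved.

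**Step 1: windows.**
- OLE entrant: 77 days.
- Completer who declines: 77 + 30 = 107 days, and 107/77 = 1.39 times as long.
- Patient who stops on day s: s + 30 days. This equals 77 at s = 47, so an earlier stop gives less counted time than an entrant has and a later stop gives more.

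**Step 2: risk per patient.** risk(d) = 1 − (1 − p)^(d/77).
- p = 50%: risk(107) = 1 − 0.5^(107/77) = 61.8%. With the off-drug hazard halved, 1 − 0.5^(92/77) = 56.3%.
- p = 30%: 39.1%, or 34.7% with the hazard halved.

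**Step 3: shift between two arms in which everyone completes.** Arm risk = e × p + (1 − e) × risk(107). The shift is therefore (e1 − e2) × [risk(107) − p], in percentage points:

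| OLE entry | p = 5% | p = 30% | p = 50% | p = 70% |
|---|---|---|---|---|
| 90% v 90% | 0 | 0 | 0 | 0 |
| 90% v 70% | 0.4 | 1.8 | 2.4 | 2.3 |
| 90% v 50% | 0.8 | 3.6 | 4.7 | 4.5 |
| 100% v 0% | 1.9 | 9.1 | 11.8 | 11.2 |

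Halving the off-drug hazard roughly halves these values (90% v 50% at p = 50%: 0.40 × 6.3 = 2.5). With 10 patients per arm, 4.7 points is 0.47 of a patient. The 100% v 0% row is an extreme bound, about 1.2 patients.

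**Step 4: direction.** Take p = 50% and an unchanged hazard. The reference arm has 90% entrants and 10% completers who decline: 0.9 × 0.50 + 0.1 × 0.618 = 51.2%. The other arm has 60% entrants, and its 40% non-entrants are one of the following:
- Completers who decline: 0.6 × 0.50 + 0.4 × 0.618 = 54.7%, a shift of **+3.5 points**.
- Day 30 stoppers (60 counted days, risk 41.7%): 0.6 × 0.50 + 0.4 × 0.417 = 46.7%, a shift of **−4.5 points**.

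The sign changes with the kind of non-entrant.

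**Step 5: event counts.** With 10% v 40% declining completers, the mean windows are 77 + 0.1 × 30 = 80 and 77 + 0.4 × 30 = 89 days. That gives 89/80 = 1.11, or 11% more events from counting time alone. With the off-drug rate halved it is 83/78.5 = 1.06, or 6%.

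**Step 6: a common on-treatment window.** Among completers it gives 77 days for everyone, and the shift in Step 3 becomes 0 at any entry rate. It does not equalize time for early stoppers. The Day 30 stopper then has 30 days against 77 (gap 47), compared with 60 against 77 now (gap 17). The gap widens for any stop before about Day 62, where 77 − s = s − 47. In the Step 4 example the arm with 40% Day 30 stoppers would show 0.6 × 0.50 + 0.4 × 0.237 = 39.5% against 50%. A rate per unit of exposure would be the same in both arms under the constant hazard.

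**The case against.** The current rule has a rationale. Entrants take open-label pitolisant the morning after Visit 5 (Protocol 3.1.1.3), so they have no off-drug period, and later events cannot be assigned to blinded treatment. Each patient contributes all follow-up before open-label drug. Entrants' later events are still listed and summarized with the OLE. This stands: cutting entrants at the last double-blind dose is sensible.

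Replacing the 30-day table outright would have a cost. It would take events soon after stopping, including serious or fatal ones, out of the main by-arm tables. It would also depart from the SAP's own TEAE definition and from the 30-day collection in Protocol 8.3.1. By Step 6, it would leave early stoppers with less counted time than now. This also stands, and the fix is shaped by it.

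The effect is small. One patient is about 10 points in an arm of 10, no formal safety testing is planned, and the entry splits used here are assumptions. Protocol 1.4 reports no evidence of withdrawal syndrome or rebound, which favours the lower off-drug hazard. All of this limits the importance of the point. None of it removes the asymmetry, which is a written rule.

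A reader might infer that an arm with more non-entrants always gets more time to record events, and so looks worse. The documents do not support that: a patient who stops before about Day 47 is counted for less time than an entrant. Nor do they establish that OLE entry depends on tolerability or benefit. They say that it is optional, subject to eligibility, and decided while the assignment is still blinded.

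**Conclusion.** The asymmetry is explicit in SAP 9.4 and 11.6.1, and it reaches the by-arm TEAE percentages and event counts. It distorts the comparison only if OLE entry or early stopping differs by arm, and the direction cannot be known in advance. Among completers, for assumed entry of 90% against 70% or 50% and a 77-day risk of 30% to 70%, the shift is about 1 to 5 points over the two hazard assumptions, half a patient or less per arm. It is below 1 point at a 5% risk, and zero if entry and stopping patterns match. It would be going too far to say that the safety comparison is invalid or biased in a known direction. This is a modest reporting weakness in a descriptive analysis, worth correcting because the correction is cheap.

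**What to change.** In SAP 9.4 and 11.6.1, before unblinding:

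1. Keep the 30-day TEAE table and footnote that entrants are counted to the last double-blind dose and non-entrants to 30 days after it.
2. Add a by-arm TEAE table with one definition for all patients, first dose through last double-blind dose, with exposure-adjusted rates. Name this table as the one for comparing arms.
3. Show non-entrants' events in the 30 days after the last dose, including serious and fatal ones, in a separate by-arm table.
4. Treat concomitant medications the same way (SAP 9.4 and 11.3.2).
5. State which window applies to early discontinuers. Protocol 3.1.1.3 and 7.2.5 must be reconciled on whether such patients can enter the OLE.

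The cost is a few extra tables and some SAP wording, and no event is lost. The on-treatment window is still shorter for early stoppers, so its crude percentages should be read together with the exposure-adjusted rates.
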